## **1.6 Adverse Effects, Warnings, and Precautions**

Given the key safety findings in the SAD (TBI-223) study, TBI-223-CL-001 and nonclinical safety studies for the cardiovascular system (prolonged QTc) and the nervous (CNS) system (tremors), we will implement the following monitoring procedures.

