- k. 12-lead safety ECGs will be printed and reviewed on-site by the Principal Investigator or designee. Triplicate ECGs will be completed at screening, Day -2, Day -1, and on Day 26 or upon early withdrawal. All other time points will be single ECG readings. ECGs may be done within 2 hours prior

Protocol TBI-223 CL-002 Version 1.0

to time of dosing and at 3, 6, 12 and 16 hours postdose on Days 1, 4, 8, 10, 12, 14, 17, and on Days 18 and 20. Another single ECG reading will be performed on the morning of Day 20 before discharge. The predose ECG should be completed within 20 minutes prior to the predose blood draw. If a subject experiences a post-dosing QTcF >500 msec with a change-from-baseline QTcF >60 msec, after repeat testing, additional ECGs should be recorded until normalization or return to baseline

- l. Predose trough blood samples will be drawn on Day 1 and daily starting on Day 4.
- m. Duplicate plasma samples will be generated from all blood pharmacokinetic samples.
- n. Postdose blood plasma samples will be drawn at the following timepoints:
  - Day 1: 0.5, 1, 2, 3, 4, 5, 6, 7, 8, 12, 16, 20, 24, 30, 36, 42, 48, 54, 60, and 72 hours. The 72-hour sample is the predose sample of Day 4.
  - Day 4: 0.5, 1, 2, 3, 4, 5, 6, 7, 8, 12, 16, 20, and 24 hours. The 24-hour sample is the predose sample of Day 5.
  - Day 17: 0.5, 1, 2, 3, 4, 5, 6, 7, 8, 12, 16, 20, 24, 30, 36, 42, 48, 54, 60, and 72 hours

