**Table 13 Schedule of Assessments (Cohort 3)**

DAY	SCREEN	CHECK-IN a	TREATMENT							CHECK OUT	FOLLOW-UP			EARLY WITHDRAWAL		
			-2	-1	1	2 - 6	7	8-13	14		17	18-22	23	30 (+1)		
EVENT																
Informed consent and medical history	X															
Check-in questions		X														
Height, weight	X															
HIV/ hepatitis B, C	X															
Serum pregnancy test b	X	X														
FSH b	X															
Urine drug/alcohol/cotinine screen	X	X														
Safety Labs (hematology, chemistry) c	X		X	X	X c		X c	X				X		X		
Coagulation d	X		X	X	X d		X d	X				X		X		
Urinalysis e	X		X	X	X e		X e	X				X				
Physical and neurological exams f	X	X	X	X	X f		Xf	X				X		X		
Vital signs (blood pressure, pulse, temperature, respiration rate, and pulse oximetry) g	X	X		X	X	X	X	X	X	X	X	X		X		
Concomitant medication review h			←-----X-----→													
Adverse events i					←-----X-----→											
Dose j				X	X	X	X	X								
12-lead safety ECGs k	X	X	X	X		X				X		X		X		
Plasma for predose trough PK l,m				X	X	X	X	X								
Plasma for Postdose PK n				X					X	X	X					

ECG = electrocardiogram; FSH = follicle-stimulating hormone; HIV = human immunodeficiency virus; PK = pharmacokinetic.

- a. Confinement to start at Check-in (evening of Day -2) and continue until 24 hours after dosing on Day 14.
- b. Serum pregnancy test at screening and at check-in for females only. FSH completed for postmenopausal females only.
- c. Blood will be collected for safety labs (hematology and chemistry) at Screening and Day -1 and at 6-7 hours postdose on Days 1, 3, 6, 10, 14, and on Day 23.
- d. Blood for coagulation testing will be collected at Screening and Day -1, and 6-7 hours postdose on Days 1, 6, 10, 14, and on Day 23.
- e. Urinalysis testing at Screening and Days -1, 1, 6, 10, 14, and 23.
- f. Neurological exam: Performed at Screening, Day -2 and Day -1 and 6-7 hours postdose and prior to blood collection for safety labs on Days 1, 3, 6, 10, 14, and on Day 23.

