- k. 12-lead safety ECGs will be printed and reviewed on-site by the Principal Investigator or designee. Triplicate ECGs will be completed at screening, Day -2, Day -1, and on Day 23 or upon early withdrawal. All other time points will be single ECG readings. ECGs may be done within 2 hours prior to time of dosing and at 3, 6, 12, and 16 hours postdose on Days 1, 2, 3, 8, 12. Another single ECG reading will be performed on the morning of Day 17 before discharge. The predose ECG should be completed within 20 minutes prior to the pre-dose blood draw. If a subject experiences a post-dosing QTcF  $>500$  msec with a change-from-baseline QTcF  $>60$  msec, after repeat testing, additional ECGs should be recorded until normalization or return to baseline
- l. Predose trough blood samples will be drawn daily starting on Day 1.
- m. Duplicate plasma samples will be generated from all blood pharmacokinetic samples.
- n. Postdose blood plasma samples will be drawn at the following timepoints:
  - Day 1: 0.5, 1, 2, 3, 4, 5, 6, 7, 8, 12, 16, 20, and 24 hours. The 24-hour sample is the predose sample of Day 2.
  - Day 14-17: 0.5, 1, 2, 3, 4, 5, 6, 7, 8, 12, 16, 20, 24, 30, 36, 42, 48, 54, 60, and 72 hours

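### Cohort 3 (3000 mg) has no ECG scheduled on Day 14, its last dose and steady-state PK day, while Cohorts 1 and 2 have a full ECG set on theirs

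*Protocol*

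**What the plan says.** Cohort 3 is dosed once daily on Days 1 to 14. Table 13 footnote k gives its on-treatment ECGs as a predose reading plus readings "at 3, 6, 12, and 16 hours postdose on Days 1, 2, 3, 8, 12". The next one is stated as follows: "Another single ECG reading will be performed on the morning of Day 17 before discharge".

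Footnote n of the same table puts the second intensive PK profile on the last dose: "Day 14-17: 0.5, 1, 2, 3, 4, 5, 6, 7, 8, 12, 16, 20, 24, 30", continuing to 72 h. On the other dosing days after Day 1 only troughs are taken: "Predose trough blood samples will be drawn daily starting on Day 1".

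For Cohorts 1 and 2, Table 12 footnote k sets predose ECGs and ECGs "at 3, 6, 12 and 16 hours postdose on Days 1, 4, 8, 10, 12, 14, 17, and on Days 18 and 20". Their steady-state PK profile (Table 12 footnote n) is "Day 17: 0.5, 1, 2, 3, 4, 5, 6, 7, 8, 12, 16, 20, 24, 30", again to 72 h. The last-dose PK day is therefore also a full ECG day in these cohorts.

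Section 1.6 names QTc prolongation as a key finding that drives the monitoring, citing "nonclinical safety studies for the cardiovascular system (prolonged QTc" in dogs among its reasons. It also says that on-treatment ECGs are to be placed near the expected Tmax.

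**The concern.** The highest dose has the thinnest ECG coverage on the day when exposure is best measured. Day 14 of Cohort 3 carries safety labs, coagulation, urinalysis, a neurological examination and serial vital signs (Table 13 footnotes c to g). The ECG is the one routine on-treatment safety assessment left out, and no reason is given.

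The QTc evidence so far is expressed by concentration. Section 1.5 excludes a QTcF effect above 10 ms only up to about 8 µg/mL of TBI-223, and section 1.7 predicts a mean steady-state Cmax of 9.7 µg/mL at 3000 mg. At that dose, no QTcF value around the steady-state peak can be set against a concentration measured at the same time. The QTcF rules in sections 1.6 and 3.2 also have no scheduled reading to act on after the Day 12 set, that is, for doses 13 and 14.

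**Working it through.** The plan gives no figure to reproduce. The check sets the ECG times in footnote k of Tables 12 and 13 against the plasma times in footnotes l and n.

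**ECGs at 3, 6, 12 and 16 h with a plasma sample at the same time, per active subject, fed dosing**

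| | Cohorts 1-2 | Cohort 3 |
|---|---|---|
| Fed intensive PK days | 4 and 17 | 1 and 14 |
| First fed dose | 4 (Day 4) | 4 (Day 1) |
| Last dose, steady state | 4 (Day 17) | 0 (Day 14) |
| Total | 8 | 4 |

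With 9 active subjects per cohort, the steady-state row is 4 × 9 = 36 pairs in each of Cohorts 1 and 2, against 0 in Cohort 3. Counting the predose reading, scheduled ECGs on the last dose day are 5 against 0.

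**Pairs that Cohort 3 does have after Day 1.** Predose ECGs on Days 2, 3, 8 and 12 pair with trough samples. The Day 17 morning ECG falls (17 − 14) × 24 = 72 h after the last dose, which is also the time of the last plasma sample. These pairs lie at 24 h and 72 h after a dose, well away from the peak: section 1.7 gives Tmax as 7 h for the SR tablet and 3 h for the IR tablet.

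**Gap.** From the 16 h reading on Day 12 to the Day 17 morning reading: (17 − 12) × 24 − 16 = 104 h.

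**Overall density.** Fed-dose serial ECG days are 4, 8, 10, 12, 14 and 17 in Cohorts 1 and 2 (6 days × 5 = 30 readings) and 1, 2, 3, 8 and 12 in Cohort 3 (5 days × 5 = 25 readings).

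**Exposure.** Predicted mean steady-state Cmax is 5.7, 7.9 and 9.7 µg/mL for Cohorts 1, 2 and 3 (section 1.7).

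- Against the rounded limit of about 8.0 µg/mL: 9.7/8.0 = 1.21 and 7.9/8.0 = 0.99.
- Against the figure of about 8.14 µg/mL, also in section 1.5: 9.7/8.14 = 1.19 and 7.9/8.14 = 0.97.

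Cohort 3 is thus 19 to 21% above the limit, and Cohort 2 is 1 to 3% below it. At the stated slope of 0.0004 ms per µg/L, the step from Cohort 2 to Cohort 3 adds 0.0004 × (9700 − 7900) = 0.72 ms from TBI-223 itself. Any contribution from the metabolite M2 is not in this figure.

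**The case against.** Several points on the other side stand.

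- Cohort 3 has serial ECGs at doses 8 and 12, probably at similar exposure. A reader might infer that the 3000 mg dose has no late ECGs under repeated dosing; that is not so.
- A reader might also infer that no ECG under repeated dosing can be matched to plasma. The trough pairs and the 72 h pair show otherwise. Only the 3 to 16 h pairs are missing.
- Adding the fasted Day 1 of Cohorts 1 and 2 to the count would widen the contrast, but Cohort 3 has no fasted day by design, so only fed days are comparable.
- The 8 µg/mL limit is where the confidence bound reaches 10 ms. It is not the edge of experience: the single-dose study extracted Holter ECGs at doses up to 2600 mg, where mean Cmax was 16.2 µg/mL and two subjects exceeded 20 µg/mL.
- The "12-lead safety ECGs" row of the Table 13 grid cannot serve as support. As extracted, the post-dose PK row is also blank on Day 14, which contradicts footnote n. The point rests on footnote k alone.
- Doses without an ECG are normal in this schedule; Cohorts 1 and 2 have none on Days 5 to 7 or 15 to 16. A post-dose reading on Day 14 could not stop that subject's dosing, and no planned escalation follows Cohort 3.

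What does not stand is the suggestion that other provisions fill the gap. Cardiac monitoring is named without a schedule, and ECGs at the investigator's discretion are not a scheduled Day 14 reading. The stopping-rule point also keeps some force. A predose ECG on Day 14 follows dose 13 and could still prevent dose 14. A later reading that met the criteria would trigger follow-up ECGs and inform any added cohort, which the protocol allows.

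**Conclusion.** The point holds as a minor, cheaply mended gap. Cohort 3 has no ECG around Tmax on its steady-state PK day and hence no 3 to 16 h ECG and plasma pair under repeated dosing: 0 against 4 per subject on that day, and 4 against 8 over fed intensive PK days. It is the only planned cohort predicted to exceed the concentration up to which a 10 ms effect was excluded.

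This assumes that footnote k, not the grid, governs the schedule, and that the simulated Cmax values are about right. The documents do not support a claim of bias or of a lost test. The protocol describes no concentration-QTc analysis for this study, and any such analysis may sit in a statistical analysis plan that is not at hand. What is lost is safety data on a named key risk at the highest dose.

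**What to change.** In Table 13 footnote k, list the serial ECG days as 1, 2, 3, 8, 12 and 14, with the same predose, 3, 6, 12 and 16 h times, and mark Day 14 in the ECG row. This raises Cohort 3 from 5 to 6 serial ECG days (25 to 30 readings), equal to the fed phase of Cohorts 1 and 2. Moving the Day 12 set to Day 14 would add no readings but would leave doses 9 to 13 without one, so adding is better.

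The cost is one footnote and one grid row, amended before Cohort 3 starts, and at most 5 single ECGs per subject (5 × 12 = 60). Plasma is already drawn at these times. Subjects are still confined at 16 h whether confinement ends on Day 17 (section 6.4) or 24 h after the Day 14 dose (Table 13 footnote a).

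The downside is practical: each ECG needs 5 minutes supine (section 6.9.6) close to PK draws with a ±2 minute window up to 24 h (Table 9), on a dense sampling day. The protocol already accepts this on Day 1 of Cohort 3 and Day 17 of Cohorts 1 and 2.

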## APPENDIX 1 PHARMACOKINETIC SAMPLE PROCESSING

### A. Collection and Processing

A more detailed description of plasma sample preparation requirements may be provided by the analytical laboratory. If such a description is provided, the method of sample preparation provided by the laboratory shall supersede those provided in this protocol and appropriate documentation shall be placed in the Investigator Site File (ISF).

Processing Instructions	
1	Samples will be collected via direct venipuncture at the time points delineated in the appropriate Events Schedule (Section 13).
2	Blood will be drawn into pre-chilled 4 mL evacuated tubes containing K 3 -EDTA and immediately placed on wet ice and then processed to plasma within 60 minutes.
3	Samples will be centrifuged at 1500 g at approximately 4°C (± 10 degrees) for 10 minutes. After centrifugation, two aliquots of plasma (the first containing at least 0.5 mL and the second containing the remainder of the plasma) will be removed and placed in appropriately labeled 5 mL polypropylene vials.
4	The aliquots will be immediately placed on dry ice. Within 90 minutes of collection, the aliquots will be stored in a freezer set at -20°C ± 10°C and remain in the freezer until transferred for analysis.
5	Samples will be transferred at the agreed upon intervals.
6	The aliquots will be transferred on dry ice to the Alliance Pharma, Inc. bioanalytical laboratory for the determination of plasma concentrations of TBI-223 and TBI-223-M2, using a validated procedure at Alliance Pharma.
7	Blood sampling, plasma processing, and storage time will be documented in the study records.

#### Labeling of aliquot tubes

Labels will contain at least the following information:

- a) Study number
- b) Subject number
- c) Period or dosing phase; sampling time (relative to dosing)
- d) Aliquot letter (A or B)

Shipment

1. The samples will be transferred to the analytical laboratory after completion of the study or at mutually agreed upon time points during the clinical conduct of the study. The second set of samples will be shipped after the bioanalytical laboratory confirms receipt of the first set of samples.
2. Samples will be packaged into cryoboxes and sorted by subject and time point.
3. Prior to shipment, the samples will be appropriately packed in a cooler containing dry ice. Sufficient dry ice will be added to ensure that the samples will remain frozen for at least 72 hours.
4. An electronic manifest will be provided in advance. The shipment will be accompanied by documentation containing the following information: name of the study drug product, protocol number, number of subjects, and number of samples included in the shipment. Expected samples that are not present will be identified.
5. All frozen pharmacokinetic samples will be transferred with accompanying documentation to:

Alliance Pharma, Inc.  
[name]  
[name]  
[contact]  
[contact]  
Contact name: [name]  
Contact e-mail: [[contact]](mailto:[contact]); [[contact]](mailto:[contact])

## APPENDIX 2 DESCRIPTION AND COMPOSITION OF TEST PRODUCT

### Description of the Dosage Form

TBI-223 tablets are supplied as immediate release (IR) or sustained release (SR) or placebo. The description of the tablets and strengths are as follows:

#### TBI-223 IR tablets 600 mg (IR)

White to off-white, capsule shaped tablets, debossed with “TBA” on one side and “22” on the other

#### TBI-223 SR Tablets, 600 mg (Prototype 1) (SR1)

White to off-white, capsule shaped tablets, debossed with “TBA” on one side and “11” on the other

#### Placebo Tablets for TBI-223 IR and SR Tablets 600 mg (Placebo)

White to off-white, capsule shaped tablets, debossed with “TBA” on one side and “17” on the other

### Composition of the Drug Product

The composition of the tablets is as follows:

#### TBI-223 IR tablets, 600 mg

TBI-223, microcrystalline cellulose, hypromellose, crospovidone, colloidal silicon dioxide, magnesium stearate

#### TBI-223 SR Tablets, 600 mg (Prototype 1) (SR1)

TBI-223, lactose monohydrate, microcrystalline cellulose, hypromellose, colloidal silicon dioxide, magnesium stearate

#### Placebo Tablets for TBI-223 IR and SR Tablets 600 mg

Microcrystalline cellulose, hypromellose, crospovidone, colloidal silicon dioxide, magnesium stearate.

### Container and Closure System

TBI-223 IR Tablets, TBI-223 SR Tablets, and Placebo Tablets are packaged as 30-count in 100 cc round high-density polyethylene (HDPE) bottles and closed with aluminum foil lined heat induction seals and 38 mm polypropylene (PP) child resistant closures (CRC).

## APPENDIX 3 DIVISION OF MICROBIOLOGY AND INFECTIOUS DISEASE TOXICITY TABLE

### Division of Microbiology and Infectious Disease (DMID) Toxicity Table

Source: *U.S. National Institute of Allergy and Infectious Diseases, DMID, November 2007 (Draft)*

**ABBREVIATIONS:** Abbreviations utilized in the Table:

ULN = Upper Limit of Normal	LLN = Lower Limit of Normal
R x = Therapy	Req = Required
Mod = Moderate	IV = Intravenous
ADL = Activities of Daily Living	Dec = Decreased

### ESTIMATING SEVERITY GRADE

For abnormalities NOT found elsewhere in the Toxicity Tables use the scale below to estimate grade of severity:

Grade	Severity Rating	Definition
GRADE 1	Mild	Transient or mild discomfort (< 48 hours); no medical intervention/therapy required.
GRADE 2	Moderate	Mild to moderate limitation in activity - some assistance may be needed; no or minimal medical intervention/therapy required.
GRADE 3	Severe	Marked limitation in activity, some assistance usually required; medical intervention/therapy required, hospitalizations possible.
GRADE 4	Potentially Life-threatening	Extreme limitation in activity, significant assistance required; significant medical intervention/therapy required, hospitalization or hospice care probable.

### SERIOUS OR LIFE-THREATENING AEs

ANY clinical event deemed by the clinician to be serious or life-threatening should be considered a grade 4 event. Clinical events considered to be serious or life-threatening include, but are not limited to: seizures, coma, tetany, diabetic ketoacidosis, disseminated intravascular coagulation, diffuse petechiae, paralysis, acute psychosis, severe depression.

### **COMMENTS REGARDING THE USE OF THESE TABLES**

- Standardized and commonly used toxicity tables (Division of AIDS, NCI's Common Toxicity Criteria (CTC), and World Health Organization (WHO)) have been adapted for use by the Division of Microbiology and Infectious Diseases (DMID) and modified to better meet the needs of Patients in DMID trials.
- For parameters not included in the following Toxicity Tables, sites should refer to the "Guide For Estimating Severity Grade" located above.

- Criteria are generally grouped by body system.
- Some protocols may have additional protocol specific grading criteria, which will supersede the use of these tables for specified criteria.

HEMATOLOGY				
	Grade 1	Grade 2	Grade 3	Grade 4
Hemoglobin	9.5 - 10.5 gm/dL	8.0 - 9.4 gm/dL	6.5 - 7.9 gm/dL	< 6.5 gm/dL
Absolute Neutrophil Count	1000-1500/mm 	750-999/mm 	500-749/mm 	<500/mm 
Platelets	75,000-99,999/mm 	50,000-74,999/mm 	20,000-49,999/mm 	<20,000/mm 
WBCs	11,000-13,000/mm 	13,000-15,000/mm 	15,000-30,000/mm 	>30,000 or <1,000/mm 
% Polymorphonuclear Leucocytes + Band Cells	> 80%	90 – 95%	>95%	-----
Abnormal Fibrinogen	Low: 100-200 mg/dL High: 400-600 mg/dL	Low: <100 mg/dL High: >600 mg/dL	Low: < 50 mg/dL -----	Fibrinogen associated with gross bleeding or with disseminated coagulation
Fibrin Split Product	20-40 mcg/ml	41-50 mcg/ml	51-60 mcg/ml	> 60 mcg/ml
Prothrombin Time (PT)	1.01 - 1.25 x ULN	1.26-1.5 x ULN	1.51 -3.0 x ULN	>3 x ULN
Activated Partial Thromboplastin (APPT)	1.01 -1.66 x ULN	1.67 - 2.33 x ULN	2.34 - 3 x ULN	> 3 x ULN
Methemoglobin	5.0 - 9.9 %	10.0 - 14.9 %	15.0 - 19.9%	> 20.0 %

CHEMISTRIES				
	Grade 1	Grade 2	Grade 3	Grade 4
Hyponatremia	130-135 mEq/L	123-129 mEq/L	116-122 mEq/L	< 116 mEq/L or abnormal sodium with mental status changes or seizures
Hypernatremia	146-150 mEq/L	151-157 mEq/L	158-165 mEq/L	> 165 mEq/L or abnormal sodium with mental status changes or seizures
Hypokalemia	3.0 - 3.4 mEq/L	2.5 - 2.9 mEq/L	2.0 - 2.4 mEq/L or intensive replacement therapy or hospitalization required	< 2.0 mEq/L or abnormal potassium with paresis, ileus or life-threatening arrhythmia

CHEMISTRIES				
	Grade 1	Grade 2	Grade 3	Grade 4
Hyperkalemia	5.6 - 6.0 mEq/L	6.1 - 6.5 mEq/L	6.6 - 7.0 mEq/L	> 7.0 mEq/L or abnormal potassium with life-threatening arrhythmia
Hypoglycemia	55-64 mg/dL	40-54 mg/dL	30-39 mg/dL	<30 mg/dL or abnormal glucose with mental status changes or coma
Hyperglycemia (non-fasting and no prior diabetes)	116 - 160 mg/dL	161 - 250 mg/dL	251 - 500 mg/dL	> 500 mg/dL or abnormal glucose with ketoacidosis or seizures
Hypocalcemia (corrected for albumin)	8.4 - 7.8 mg/dL	7.7 - 7.0 mg/dL	6.9 - 6.1 mg/dL	< 6.1 mg/dL or abnormal calcium with life threatening arrhythmia or tetany
Hypercalcemia (correct for albumin)	10.6 - 11.5 mg/dL	11.6 - 12.5 mg/dL	12.6 - 13.5 mg/dL	> 13.5 mg/dL or abnormal calcium with life threatening arrhythmia
Hypomagnesemia	1.4 - 1.2 mEq/L	1.1 - 0.9 mEq/L	0.8 - 0.6 mEq/L	< 0.6 mEq/L or abnormal magnesium with life-threatening arrhythmia
Hypophosphatemia	2.0 - 2.4 mg/dL	1.5 -1.9 mg/dL or replacement Rx required	1.0 -1.4 mg/dL intensive therapy or hospitalization required	< 1.0 mg/dL or abnormal phosphate with life-threatening arrhythmia
Hyperbilirubinemia (when accompanied by any increase in other liver function test)	1.1 - <1.25 x ULN	1.25 - <1.5 x ULN	1.5 – 1.75 x ULN	> 1.75 x ULN
Hyperbilirubinemia (when other liver function are in the normal range)	1.1 - <1.5 x ULN	1.5 - <2.0 x ULN	2.0 – 3.0 x ULN	> 3.0 x ULN
BUN	1.25 - 2.5 x ULN	2.6 - 5 x ULN	5.1 - 10 x ULN	> 10 x ULN
Hyperuricemia (uric acid)	7.5 – 10.0 mg/dL	10.1 – 12.0 mg/dL	12.1 – 15.0 mg/dL	>15.0 mg/dL
Creatinine	1.1 - 1.5 x ULN	1.6 - 3.0 x ULN	3.1 - 6 x ULN	> 6 x ULN or dialysis required

ENZYMES				
	Grade 1	Grade 2	Grade 3	Grade 4
AST (SGOT)	1.1 - <2.0 x ULN	2.0 – <3.0 x ULN	3.0 – 8.0 x ULN	> 8 x ULN
ALT (SGPT)	1.1 - <2.0 x ULN	2.0 – <3.0 x ULN	3.0 – 8.0 x ULN	> 8 x ULN

ENZYMES				
	Grade 1	Grade 2	Grade 3	Grade 4
GGT	1.1 - <2.0 x ULN	2.0 – <3.0 x ULN	3.0 – 8.0 x ULN	> 8 x ULN
Alkaline Phosphatase	1.1 - <2.0 x ULN	2.0 – <3.0 x ULN	3.0 – 8.0 x ULN	> 8 x ULN
Amylase	1.1 - 1.5 x ULN	1.6 - 2.0 x ULN	2.1 - 5.0 x ULN	> 5.1 x ULN
Lipase	1.1 - 1.5 x ULN	1.6 - 2.0 x ULN	2.1 - 5.0 x ULN	> 5.1 x ULN

URINALYSIS				
	Grade 1	Grade 2	Grade 3	Grade 4
Proteinuria	1+ or 200 mg - 1 gm loss/day	2-3+ or 1- 2 gm loss/day	4+ or 2-3.5 gm loss/day	nephrotic syndrome or > 3.5 gm loss/day
Hematuria*	microscopic only <10 rbc/hpf	gross, no clots >10 rbc/hpf	gross, with or without clots, OR red blood cell casts	obstructive or required transfusion

\*Assessment does not apply if a subject is on menses.

CARDIOVASCULAR				
	Grade 1	Grade 2	Grade 3	Grade 4
Cardiac Rhythm		asymptomatic, transient signs, no Rx required	recurrent/persistent; symptomatic Rx required	unstable dysrhythmia; hospitalization and treatment required
Hypertension	transient increase > 20 mm/Hg; no treatment 	recurrent, chronic increase > 20mm/Hg. /treatment required	acute treatment required; outpatient treatment or hospitalization possible	end organ damage or hospitalization required
Hypotension	transient orthostatic hypotension with heart rate increased by <20 beat/min or decreased by <10 mm Hg systolic BP, No treatment required 	symptoms due to orthostatic hypotension or BP decreased by <20 mm Hg systolic; correctable with oral fluid treatment	requires IV fluids; no hospitalization required	mean arterial pressure <60mm/Hg or end organ damage or shock; requires hospitalization and vasopressor treatment

CARDIOVASCULAR				
	Grade 1	Grade 2	Grade 3	Grade 4
Pericarditis	minimal effusion	mild/moderate asymptomatic effusion, no treatment	symptomatic effusion; pain; EKG changes	tamponade; pericardiocentesis or surgery required
Hemorrhage, Blood Loss	microscopic/occult	mild, no transfusion	gross blood loss; 1-2 units transfused	massive blood loss; > 3 units transfused

RESPIRATORY				
	Grade 1	Grade 2	Grade 3	Grade 4
Cough	Transient - no treatment	persistent cough; treatment responsive	Paroxysmal cough; uncontrolled with treatment	-----
Bronchospasm, Acute	transient; no treatment; 70% - 80% FEV 1 of peak flow	requires treatment; normalizes with bronchodilator; FEV 1 50% - 70% (of peak flow)	no normalization with bronchodilator; FEV 1 25% - 50% of peak flow; or retractions present	cyanosis: FEV 1 < 25% of peak flow or intubation necessary
Dyspnea	dyspnea on exertion	dyspnea with normal activity	dyspnea at rest	dyspnea requiring Oxygen therapy

GASTROINTESTINAL				
	Grade 1	Grade 2	Grade 3	Grade 4
Nausea	mild or transient; maintains reasonable intake	moderate discomfort; intake decreased significantly; some activity limited	no significant intake; requires IV fluids	hospitalization required;
Vomiting	1 episode in 24 hours	2-5 episodes in 24 hours	>6 episodes in 24 hours or needing IV fluids	physiologic consequences requiring hospitalization or requiring parenteral nutrition
Constipation	requiring stool softener or dietary modification	requiring laxatives	obstipation requiring manual evacuation or enema	obstruction or toxic megacolon
Diarrhea	mild or transient; 3-4 loose stools/day or mild diarrhea	moderate or persistent; 5-7 loose stools/day or	>7 loose stools/day or bloody diarrhea; or orthostatic	hypotensive shock or physiologic consequences

GASTROINTESTINAL				
	Grade 1	Grade 2	Grade 3	Grade 4
	last < 1 week	diarrhea lasting >1 week	hypotension or electrolyte imbalance or >2L IV fluids required	requiring hospitalization
Oral Discomfort/Dysphagia	mild discomfort; no difficulty swallowing	some limits on eating/drinking	eating/talking very limited; unable to swallow solid foods	unable to drink fluids; requires IV fluids

NEUROLOGICAL				
	Grade 1	Grade 2	Grade 3	Grade 4
Neuro-Cerebellar	slight incoordination dysdiadochokinesia	intention tremor, dysmetria, slurred speech; nystagmus	locomotor ataxia	incapacitated
Psychiatric	mild anxiety or depression	moderate anxiety or depression; therapy required; change in normal routine	severe mood changes requiring therapy; or suicidal ideation; or aggressive ideation	acute psychosis requiring hospitalization; or suicidal gesture/attempt or hallucinations
Muscle Strength	Subjective weakness no objective symptoms/ signs	mild objective signs/symptoms no decrease in function	objective weakness function limited	paralysis
Paresthesia (burning, tingling, etc.)	mild discomfort; no treatment required	moderate discomfort; non-narcotic analgesia required	severe discomfort; or narcotic analgesia required with symptomatic improvement	incapacitating; or not responsive to narcotic analgesia
Neuro-sensory	mild impairment in sensation (decreased sensation, e.g., vibratory, pinprick, hot/cold in great toes) in focal area or symmetrical distribution; or change in taste, smell, vision and/or hearing	moderate impairment (mod decreased sensation, e.g., vibratory, pinprick, hot/cold to ankles) and/or joint position or mild impairment that is not symmetrical	severe impairment (decreased or loss of sensation to knees or wrists) or loss of sensation of at least mod degree in multiple different body areas (i.e., upper and lower extremities)	sensory loss involves limbs and trunk; paralysis; or seizures

MUSCULOSKELETAL				
	Grade 1	Grade 2	Grade 3	Grade 4
Arthralgia (joint pain)	mild pain not interfering with function	moderate pain, analgesics and/or pain interfering with function but not with activities of daily living	severe pain; pain and/or analgesics interfering with activities of daily living	disabling pain
Arthritis	mild pain with inflammation, erythema or joint swelling – but not interfering with function	moderate pain with inflammation, erythema or joint swelling – interfering with function, but not with activities of daily living	severe pain with inflammation, erythema or joint swelling –and interfering with activities of daily living	permanent and/or disabling joint destruction
Myalgia	myalgia with no limitation of activity	muscle tenderness (at other than injection site) or with moderate impairment of activity	severe muscle tenderness with marked impairment of activity	frank myonecrosis

SKIN				
	Grade 1	Grade 2	Grade 3	Grade 4
Mucocutaneous	erythema; pruritus	diffuse, maculo papular rash, dry desquamation	vesiculation or moist desquamation or ulceration	exfoliative dermatitis, mucous membrane involvement or erythema, multiforme or suspected Stevens-Johnson or necrosis requiring surgery
Induration	< 15mm	15-30 mm	>30mm	
Erythema	< 15mm	15-30 mm	>30mm	
Edema	< 15mm	15-30 mm	>30mm	
Rash at Injection Site	< 15mm	15-30 mm	>30mm	
Pruritus	slight itching at injection site	moderate itching at injection extremity	itching over entire body	

SYSTEMIC				
	Grade 1	Grade 2	Grade 3	Grade 4
Allergic Reaction	pruritus without rash	localized urticaria	generalized urticaria; angioedema	anaphylaxis
Headache	mild, no treatment required	transient, moderate; treatment required	severe; responds to initial narcotic therapy	intractable; requires repeated narcotic therapy
Fever: oral	37.7 - 38.5 C or 100.0 - 101.5 F	38.6 - 39.5 C or 101.6 - 102.9 F	39.6 - 40.5 C or 103 - 105 F	> 40 C or > 105 F
Fatigue	normal activity reduced < 48 hours	normal activity decreased 25- 50% > 48 hours	normal activity decreased > 50% can't work	unable to care for self
